7.3.6 Selected Labs and MELD Scores Summarized by Visit

Changes in selected lab values and disease severity scores that have been demonstrated to correlate with survival will be presented for the ITT population. Differences between treatment groups at each time point will be analyzed based on a mixed model repeated measure (MMRM) with fixed effects of treatment group, visit and the treatment group by visit interaction, and a covariate of baseline value for the corresponding treatment. An unstructured covariance matrix will be used. If the model does not converge with an unstructured covariance matrix due to insufficient data at some visits, the spatial power covariance structure will be used. In addition, one sample t-test will be used to test if change from baseline value is zero at each time point within treatment group. All changes will be calculated relative to randomization date/time (as all subjects are on standard of care treatment as of the randomization date/time). Additional summaries of changes relative to ELAD start date/time will be provided for selected analyses. For comparative purpose, the Control group will be summarized by changes relative to End of Study Day 2, as this most closely mimics the time of initiation of ELAD treatment in those subjects randomized to ELAD. If Study Day 2 is missing for Control subjects, the last non-missing visit before Study Day 2 will be used for analysis.

As a sensitivity analysis, the analyses will be repeated after the missing data is imputed using the last observation carried forward (LOCF) approach. These will include:

- MELD;
- Total Bilirubin;
- Creatinine;
- INR;
- Sodium.

The values for MELD, Total Bilirubin, Creatinine, INR and Sodium will be displayed in a listing.

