5.5 EVALUATIONS WHILE ON TREATMENT

All evaluations in this section are for both ELAD and Control subjects, unless specified otherwise.

5.5.1 Daily Evaluations through End of Study Day 7

The following procedures will be performed daily through End of Study Day 7, based on 24-hour periods following the End of Study Day 1, and must be performed a minimum of 12 hours apart and, if specified, either within the defined time window or during the Study Day. Any subject discharged from the hospital prior to End of Study Day 7 must return to the study site for the End of Study Day 7 evaluation only (+2 days). It is not necessary to have outpatients return for daily assessments. There may be instances where the ELAD treatment period is delayed; therefore daily evaluations may be extended beyond End of Study Day 7. Additional eCRFs may be added in this situation. See [Table 2](#) for evaluations schedules for Control subjects and [Table 3](#) for ELAD subjects:

- Physical examination (performed by a Physician, Physician Assistant, or Nurse Practitioner if within the scope of practice for institution)
- Vital signs (blood pressure, heart rate, respiration rate, temperature)
- Encephalopathy stage [West Haven Criteria, performed by a study physician, Physician Assistant, or Nurse Practitioner if within the scope of practice for institution (Refer to [Appendix A](#))] unless subject is sedated
- Routine laboratory evaluations: BUN, creatinine, glucose, sodium, potassium, chloride, carbon dioxide (or bicarbonate), calcium, magnesium, phosphate, ALT, AST, bilirubin (total/direct), albumin, total protein, alkaline phosphatase
- Additional laboratory evaluations: ammonia, lactate, α -fetoprotein, lactate dehydrogenase (LDH)
- Complete Blood Count (CBC): white blood cell count (WBC), hematocrit, hemoglobin, and platelets
- Blood collection for outside analysis (consented subjects at participating centers only - at End of Study Days 3, 5, and 7) (See [Section 5.6.3](#))
- Blood culture samples $\times 2$ – at End of Study Day 2 and End of Study Day 4 for Control subjects, or within 6 hours prior to ELAD treatment start and Hours 48 and 96 of treatment for ELAD subjects
- Ultrafiltrate samples must be drawn as described in [Section 5.6.2](#) and [Section 5.6.4](#).
- PT, PTT, and INR (If heparin is administered, PTT will be assayed in accord with the standard anticoagulation therapy protocol at the site.)

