1.2.3 Exploratory Objectives

The exploratory objectives will identify potential differences between treatment groups in factors related to liver transplant, standard demographics, selected baseline characteristics, medical history, and standard of care. These factors are pre-specified in this SAP, and are based on previously identified and medically pertinent influences on treatment outcomes in alcoholic hepatitis, as well as on factors shown to be important in prior studies of ELAD. In addition, the relationship between outcomes and ELAD System performance, therapeutic interventions of interest, and administration of concomitant pharmacotherapies of interest will be assessed in order to help inform product labeling and use. Analyses of post-treatment medical care and behavior will also be carried out to assess whether there are differences between ELAD-treated and Control subjects and whether those differences have an impact on treatment outcomes. Furthermore, the difference between treatment groups at each time point of selected labs and MELD scores with a mixed model repeated measure (MMRM) will be analyzed. Changes in certain biomarkers of interest will also be evaluated (See [Section 7.3](#)).

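### The MMRM for MELD and laboratory values has one baseline slope for all visits, and its only fallback covariance assumes equal variance at every visit

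*SAP*

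**What the plan says.** SAP 1.2.3 lists this analysis among the exploratory objectives: "the difference between treatment groups at each time point of selected labs and MELD scores with a mixed model repeated measure (MMRM) will be analyzed". SAP 7.3.6 gives the mean model as "fixed effects of treatment group, visit and the treatment group by visit interaction, and a covariate of baseline value for the corresponding treatment". No baseline-by-visit term is listed. The covariance choice is "An unstructured covariance matrix will be used", and if that model fails to converge "due to insufficient data at some visits, the spatial power covariance structure will be used". There is no second fallback, and neither a robust variance nor a degrees-of-freedom method is named. Within-arm changes are tested outside the model: a "one sample t-test will be used to test if change from baseline value is zero at each time point within treatment group".

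SAP 7.3.6 does not list the visits that enter the model. Protocol 5.5.1 says "The following procedures will be performed daily through End of Study Day 7", and Protocol 5.5.4 and 5.5.5 add Days 14, 21, 28, 63 and 91. For discharged subjects, Protocol 5.5.1 says "It is not necessary to have outpatients return for daily assessments", although they must come back for Day 7.

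**The concern.** There are two separate weaknesses.

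**Single baseline slope.** Baseline laboratory values are taken within 24 hours before randomization (Protocol 5.2.3), and Study Day 1 ends at the next morning's draw (Protocol 5.4). The same coefficient must therefore describe a repeat test about a day later and a value three months later. The first slope should be near 1 and the second much smaller. A compromise slope over-adjusts late visits for any chance baseline difference between the arms.

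**Fallback covariance.** Spatial power sets the covariance of visits i and j to σ²ρ^|ti−tj|, so σ² is the same at every visit. Given baseline, there is little room for spread at Day 1, and entry limits on MELD, INR and creatinine narrow the starting range. By Day 91 some survivors will have recovered and others will not. If the spread does grow, a pooled variance is too large early and too small late.

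What is at stake is the between-arm comparison at each time point, which is the purpose of the section.

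**Working it through.** The documents give no SD, correlation or precision for this model, so there is no plan figure to reproduce. The check is a simulation whose slopes and SDs are assumptions, shown as a range.

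**Inputs from the documents**
- 75 subjects per arm (SAP 1.3).
- 12 visits: Days 1-7, 14, 21, 28, 63 and 91 (Protocol 5.5). An unstructured matrix then has 12 × 13 / 2 = 78 parameters.
- Hazards of 0.004/day for Control and 0.4 × 0.004 = 0.0016/day for ELAD (Protocol 7.1). Expected alive at Day 91: 75·exp(−0.364) = 52 and 75·exp(−0.1456) = 65, about 117 of 150.

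**Assumed scenarios** (baseline SD = 1)
- A: slope 0.97 at Day 1 falling to 0.05 at Day 91; residual SD 0.29 rising to 1.01 (1.01/0.29 = 3.5-fold).
- B: slope 0.98 falling to 0.22; residual SD 0.82 rising to 3.01 (3.7-fold).
- C: slope 0.6 and residual SD 1.0 throughout.
- D: slope 0.98 falling to 0.10; residual SD 1.00 falling to 0.50.

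Each scenario had 500 simulated trials, with death as dropout. The table gives the mean model SE of the by-visit treatment difference divided by its true SD, with the SAP's single baseline slope. Monte Carlo error on a ratio is about 1/√(2 × 500) = 3%.

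| Scenario | Covariance | Day 1 | Day 7 | Day 28 | Day 91 | Coverage Day 1 / Day 91 |
|---|---|---|---|---|---|---|
| A | unstructured | 0.96 | 0.99 | 0.98 | 1.02 | 94% / 97% |
| A | spatial power | 1.61 | 1.33 | 0.97 | 0.89 | 100% / 91% |
| B | unstructured | 0.95 | 0.99 | 0.97 | 0.99 | 93% / 94% |
| B | spatial power | 2.73 | 1.38 | 0.92 | 0.89 | 100% / 91% |
| C | unstructured | 0.95 | 0.97 | 0.98 | 1.00 | 93% / 94% |
| C | spatial power | 0.95 | 0.97 | 0.98 | 1.03 | 93% / 95% |
| D | unstructured | 1.00 | 1.03 | 1.00 | 1.00 | 95% / 96% |
| D | spatial power | 0.68 | 0.96 | 1.28 | 1.27 | 81% / 99% |

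**Cost of the single slope, unstructured matrix.** The true SD of the Day-91 difference, single slope against baseline-by-visit, is:
- A: 0.231 / 0.186 = 1.24
- B: 0.556 / 0.539 = 1.03
- C: no loss, because the slope is constant
- D: 0.101 / 0.092 = 1.10

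The reason can be checked by hand. In A and B the fitted common slope was 0.88 and 0.96, close to the early slopes because early visits have the smallest residual variance. At Day 91 it is therefore wrong by 0.88 − 0.05 = 0.83 and 0.96 − 0.22 = 0.74. The chance baseline difference between arms has SD √(2/75) = 0.163. The resulting mis-adjustment has SD 0.83 × 0.163 = 0.135 and 0.74 × 0.163 = 0.121. Adding variances gives √(0.186² + 0.135²) = 0.230 and √(0.539² + 0.121²) = 0.552, which match the simulated 0.231 and 0.556 closely. The mis-adjustment and the lost precision are thus one cost seen twice, and should not be added together.

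**Effect of the fallback on early power.** A difference with 80% power under a correct SE keeps P(Z > 1.96r − 2.80) when the SE is inflated by r.
- Day 3, r = 1.50 (A) and 1.91 (B): P(Z > 0.14) = 44% and P(Z > 0.94) = 17%.
- Day 7, r = 1.33 (A) and 1.38 (B): P(Z > −0.19) = 58% and P(Z > −0.10) = 54%.

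**Do the repairs work?** Baseline-by-visit with an unstructured matrix gave ratios of 0.95-1.03 at the tabulated visits in all four scenarios. Adding the interaction does not repair spatial power: in A and B the ratio is then 2.8-3.0 at Day 1 and 0.87-0.89 at Day 91. In separate null simulations with assumed rising SD, 75 per arm and a hazard of 0.003/day, sandwich standard errors on spatial-power fits held type I error at 4-6% at every visit.

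**The case against.** A reader might infer that this MMRM will give error bars that are too wide early and too narrow late. The documents do not support that. The planned matrix is unstructured, and with it the standard errors are right in every scenario, single slope included. The distortion needs two further conditions: the fallback must be triggered, and residual variance must grow.

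Neither condition is established. Fitting 78 parameters with about 117 of 150 subjects alive at Day 91 is demanding, but no failure rate was measured, and the visit list itself is inferred from the protocol. No document gives an SD by visit, so growth is a clinical expectation; scenarios C and D show no distortion and the reverse distortion.

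A reader might also infer that the fallback would hide ELAD's early effect. The largest inflation is at Day 1, before ELAD normally starts: SAP 7.3.6 itself takes the end of Study Day 2 as the closest match to ELAD initiation. Early bilirubin is also tested outside this model, by chi-squared at Day 7 (SAP 7.2.2, with further cut-offs in 7.3.4). The one-sample t-tests use each visit's own SD. The LOCF repeat fills in missing visits, so it is less likely to need the fallback.

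Spatial power also has a merit: it respects unequal visit spacing. Heterogeneous Toeplitz or first-order autoregressive structures would treat Day 28 to 63 like Day 1 to 2.

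All of this limits the point without removing it. The SAP itself foresees sparse visits and writes a rule for them, so that rule should be sound when used. The single slope costs late precision whether or not the unstructured model converges, provided the slope falls.

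**Conclusion.** The point stands in a limited, partly conditional form.

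- **Single slope:** it loses late precision if the baseline slope falls with time, which is very probable given when baseline is taken. The Day-91 SD was 3-24% larger in the assumed growing-variance scenarios. Inference under the unstructured matrix remains valid.
- **Fallback:** if it is used and the residual SD grows about 3.5-fold, standard errors are roughly 1.6-2.7 times too large at Day 1 and 1.3-1.4 times at Day 7. At Day 91 they are about 11% too small, with coverage near 91%. The early effect is large and the late effect modest.

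These sizes rest on assumed slopes and SDs. The analysis is exploratory. The log-rank test of overall survival and the secondary efficacy tests do not depend on it. This is a cheap improvement worth making, not a threat to the trial's main conclusion.

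**What to change.** In SAP 7.3.6:

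1. Add a baseline-by-visit interaction to the fixed effects. This replaces 1 slope with 12, so it uses 11 more degrees of freedom.
2. For any covariance other than unstructured, use empirical (sandwich) standard errors. Preferably also replace the fallback with a structure that has visit-specific variances and respects the unequal spacing. First-order ante-dependence is one option: 12 variances plus 11 adjacent-visit correlations, 23 parameters instead of 78. Sandwich standard errors correct the SE but not an estimate affected by dropout under a wrong covariance, which is why the better structure is worth having too.
3. List the visits that enter the model and name the degrees-of-freedom method.
4. Clarify what a baseline value for the corresponding treatment means. It could be read as a separate slope per arm; on no reading is it a baseline-by-visit term.

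The cost is a few sentences and a few program options, with no new data.

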7.3.7 Outcome relative to Infection, Fluid Overload/Fluid Loss and Bleeding

Proportion of survivor tables at Study Day 28 and at Study Day 91 will be presented by treatment group and by infection. Ongoing infection at Randomization, infection which emerged as a TESAE between Randomization and Day 7, between Day 8 and Day 14 and between Day 15 and Day 28, will be summarized separately. Proportion of survivors at Study Day 91 will be summarized by treatment group by subjects who developed an infection TESAE between Day 29 and Day 91. Differences between treatment groups within each infection group will be analyzed based on a Chi-squared test. Additionally, differences between infection group, regardless of treatment, will be analyzed based on a Chi-square test.

Proportion of survivor tables at Study Day 28 and at Study Day 91 will be presented by treatment group and by occurrence of fluid overload or loss events. Fluid overload or loss events which emerged as a TESAE between Randomization and Day 7, between Day 8 and Day 14, and between Day 15 and Day 28, will be summarized separately. Proportion of survivors at Study Day 91 will be summarized by treatment group by subjects who developed a fluid overload or loss event TESAE between Day 29 and Day 91. Differences between treatment groups within each fluid overload or loss group will be analyzed based on a Chi-squared test. Additionally, differences between fluid overload or loss group, regardless of treatment, will be analyzed based on a Chi-square test.

Proportion of survivor tables at Study Day 28 and at Study Day 91 will be presented by treatment group and by occurrence of bleeding. Bleeding which emerged as a TESAE between Randomization and Day 7, between Day 8 and Day 14, and between Day 15 and Day 28, will be summarized separately. Proportion of survivors at Study Day 91 will be summarized by treatment group by subjects who developed a bleeding TESAE between Day 29 and Day 91. Differences between treatment groups within each bleeding group will be analyzed based on a Chi-squared test. Additionally, differences between bleeding group, regardless of treatment, will be analyzed based on a Chi-square test.

Subjects that die, are lost to follow up or withdraw from the study during one of these periods will not be included in the summaries covering subsequent periods for the above analyses.

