5.5.8 Missed Visits

If a subject misses a scheduled appointment, every effort should be made to reach the subject by the study site personnel. The missed visit should be communicated to the home visit provider and a concerted effort should be made to contact the subject. If the subject does not return messages after at least 3 attempts, and a back-up contact was identified, every effort should be made to reach the back-up contact.

If the back-up contact cannot be reached by phone after at least 3 attempts, a registered letter will be sent by the study site personnel to both the study subject and to the back-up contact, requesting that they call the site to reconfirm contact information.

If no information is forthcoming within three weeks of sending the registered letters, the subject will be considered lost to follow-up. If at a later time, the subject contacts the study site, or survival information is made known, the study visit should be done at that time (or as much of it as possible; i.e. documentation of survival outcome), even if it is outside the study window. If the back-up contact responds, effort should be made to get the subject's current contact information and confirm outcome, if possible.

The site should look in their medical records for any information regarding possible death of the subject if they get no response to calls. All deaths will be documented on the eCRFs. Deaths that occur during the subject's active participation in VTL-308 will be reported as an outcome of an SAE.

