All suspected unexpected serious adverse reactions (SUSARs) related (related is defined as possibly related, probably related, and related) to the investigational product which occur during this study are subject to expedited reporting.

All adverse events, regardless of severity, and whether or not related to the study treatment, will be recorded in the appropriate section of the eCRF.

All adverse events beginning after the discontinuation of treatment with the ELAD System, whether serious or non-serious and regardless of relatedness to the study treatment, must be reported to the Sponsor if the onset of the adverse event occurred during the subject's study

participation (from Randomization through the last day of study participation or through Study Day 91).

All serious adverse events that are unexpected (defined as an adverse event not listed in the [Investigator's Brochure](#)) and related (related is defined as possibly related, probably related, and related) to the investigational product that occur from Randomization through the last day of study participation or through Study Day 91 must be reported to the Sponsor in a timely fashion.

Any death or liver transplant occurring from Randomization through the last day of study participation or through Study Day 91, must be reported to the Sponsor regardless of how much time has elapsed since the last exposure to investigational product treatment. The cause of death must be reported as an SAE, since death is an outcome and not an SAE. A death occurring after Study Day 91 that is not reasonably associated with investigational product treatment does not require completion of an SAE reporting form. However, both of these events should trigger completion of applicable VTL-308E eCRFs for the subject (see [Section 13](#)).

If progression of the underlying disease (i.e., the condition being treated with the investigational product) might be reasonably anticipated given the nature and severity of the underlying disease, then progression of the underlying disease per se will not constitute an adverse event. However, if the progression of the underlying disease meets the criterion for “serious” categorization of adverse events (e.g., the underlying disease results in premature death or prolonged hospitalization), then it should be reported as an SAE.

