Appendix C Fluid Overload/Fluid Loss Symptoms Search Terms

Ascites

Oesophageal varices haemorrhage

Upper gastrointestinal haemorrhage

Generalised oedema

Oedema peripheral

Edema without specification

Acute respiratory distress syndrome

Acute respiratory failure

Hypoxia

Pleural effusion

Pulmonary oedema

Respiratory arrest

Respiratory failure

Renal failure (any type)

Hypotension (any type)

Shock (any type)

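### SAP 7.3.7 tests survival between event groups that a death can help define, so its chi-square tests can reject well above 5% with no effect of the event, chiefly Days 29–91 against Day 91 and Days 15–28 against Day 28

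*SAP*

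**What the plan says.** SAP 7.3.7 forms groups from serious treatment-emergent events. For the fluid category: "Fluid overload or loss events which emerged as a TESAE between Randomization and Day 7, between Day 8 and Day 14", then Days 15–28, each set against Day 28 and Day 91 survival. For the last window, Day 91 survival "will be summarized by treatment group by subjects who developed a fluid overload or loss event TESAE between Day 29 and Day 91". Infection and bleeding follow the same pattern, using the term lists in Appendices B to D. ELAD and Control are compared within each event group, and the event groups are also compared with the arms pooled: "Additionally, differences between fluid overload or loss group, regardless of treatment, will be analyzed based on a Chi-square test".

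Subjects who die, withdraw or are lost during a window "will not be included in the summaries covering subsequent periods for the above analyses". They are removed from later windows only, so a death counts in the window where it occurs.

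Protocol 9.4 states: "The cause of death must be reported as an SAE, since death is an outcome and not an SAE". Protocol 5.5.8 says that deaths during active participation "will be reported as an outcome of an SAE". Section 9.4 also covers fatal disease: "if the progression of the underlying disease meets the criterion for" seriousness, it is reported as an SAE.

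The lists contain terms that can describe the manner of dying: septic shock (Appendix B); respiratory arrest, respiratory failure, renal failure and shock (Appendix C); exsanguination and haemorrhagic shock (Appendix D).

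**The concern.** A chi-square test of survival by group takes group membership as settled before the outcome. Here a subject who dies can enter the event group because the fatal condition had to be recorded as an SAE. A survivor has no such route. The overlap is complete in two tables, Days 15–28 against Day 28 survival and Days 29–91 against Day 91 survival, because grouping and outcome use the same days.

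The SAP avoids this elsewhere. The early bilirubin analysis (7.2.2) drops deaths through Day 7, and the Lille analysis (7.3.5) drops deaths on or before the evaluation day. Section 7.3.7 has no such rule.

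At stake is how these complications are read. SAP 8.3.1 only counts and lists them; 7.3.7 is where survival is tested against them. SAP 1.2.3 intends some of the exploratory outcome work to inform labeling and use. An association produced partly by how deaths are recorded could be taken as evidence that a complication worsens survival.

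**Working it through.** Section 7.3.7 gives no operating characteristic to reproduce and no significance level; 5% two-sided is assumed, as for the log-rank test.

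**Inputs from the documents**
- 75 subjects per arm (Protocol 7.1, SAP 1.3).
- Control hazard 0.004 per day and hazard ratio 0.4 (Protocol 7.1), so the ELAD hazard is 0.0016. Check: ln 2/0.004 = 173 days and ln 2/0.0016 = 433 days, against the stated medians of about 175 and 438.
- SAP 1.3 implies lower hazards: −ln(0.40)/365 = 0.0025 and −ln(0.48)/365 = 0.0020 per day in Control.

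**Assumptions, because the documents give neither figure**
- Background risk of a listed event of 15% per full window, independent of death and cut off at death.
- A share c of deaths with a listed fatal SAE, shown from 10% to 70%. The share applies separately to each of the three lists.

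**Expected deaths under Protocol hazards**
- Days 29–91: 75(e^−0.112 − e^−0.364) + 75(e^−0.0448 − e^−0.1456) = 14.9 + 6.9 = 21.8, among 138.8 alive at Day 28.
- Days 15–28: 75(e^−0.056 − e^−0.112) + 75(e^−0.0224 − e^−0.0448) = 3.9 + 1.6 = 5.5, among 144.2 alive at Day 14.

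**Expected table, Days 29–91 against Day 91, c = 50%**
- Survivors: 138.8 − 21.8 = 117.0. Of these, 15% = 17.5 have an event and 99.5 do not.
- Deaths: 10.9 carry a listed fatal SAE. Of the other 10.9, about 7.7% (1 − 0.15/−ln 0.85, the average over part-windows) had a background event, or 0.8. That gives 11.7 with and 10.1 without.
- Apparent survival: 17.5/29.2 = 60% with the event and 99.5/109.6 = 91% without, although the background event has no effect.
- Chi-square on these counts: 138.8 × (11.7 × 99.5 − 17.5 × 10.1)² / (29.2 × 109.6 × 21.8 × 117.0) ≈ 16.6, against a critical value of 3.84.

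**Simulated rejection rates** (exponential deaths, arms pooled, Protocol hazards)

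| Share c | 10% | 30% | 50% | 70% |
|---|---|---|---|---|
| Days 29–91 vs Day 91, onset at death | 7% | 59% | 96% | 100% |
| Days 15–28 vs Day 28, onset at death | 6% | 29% | 61% | 86% |
| Days 29–91 vs Day 91, mean 7-day lag | 5% | 47% | 90% | 100% |
| Days 15–28 vs Day 28, mean 7-day lag | 3% | 12% | 25% | 41% |

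The lag rows let the fatal SAE start before death by an exponential time of mean m = 7 days (assumed). For a window of w days, the proportion starting in the same window as the death is about 1 − (m/w)(1 − e^(−w/m)): 89% for 63 days and 57% for 14 days. This is why the shorter window gains more from the lag.

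At a hazard of 0.0023, inside the SAP range, with ratio 0.4 and no lag, shares of 30/50/70% give 45/88/99% and 26/49/73%.

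**Where the effect is small or reversed**
- Randomization–Day 7 and Days 8–14 against Day 91: about 6–9% at shares of 30–50%.
- c = 0, Days 29–91: deaths with an event are 21.8 × 0.077 = 1.7, so survival is 17.5/19.2 = 91% with the event and 99.5/119.6 = 83% without. The bias reverses, because subjects who die have less time to record an event.

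**Landmark check.** Keeping only subjects alive at window end and looking at later survival gives 3.5–5.6% rejection, with background risks of 10–30% and shares from 0 to 100%, no lag.

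**The case against.** The strongest reply has four parts.

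- **Windows follow onset.** A reader might infer that every fatal SAE falls in the same window as the death. The documents do not say so. Protocol 9.4 requires the cause to be reported and does not mention windows, while SAP 8.3 defines treatment-emergent events by onset. A fatal infection that starts on Day 12 and kills on Day 20 belongs to Days 8–14. This stands. It weakens the Days 15–28 result considerably and the Days 29–91 result only a little.
- **The share is unknown.** Only deaths with a listed cause are affected. Hepatic failure and multi-organ failure are on none of the lists, so a death from progression of liver disease need not enter any group. At a 10% share the rates are near nominal. This stands, and it is why a range is shown.
- **Some of the association may be real.** If septic shock caused the death, the link is not an artefact. The simulation treats every listed fatal SAE as a label only. This stands as a limit on interpretation. It does not rescue the test, which cannot separate the two.
- **The analysis is exploratory.** SAP 7.3 places it there and no conclusion on the primary or secondary endpoints rests on it. This stands and limits the weight of the point.

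A reader might also infer that all the tables will show harm whatever the truth. The small early-window rates and the reversal at a very low share rule that out. Infection already ongoing at randomization is a baseline group and is unaffected. The ELAD–Control tests within event groups also compare subjects selected partly by death, but that effect has not been sized here.

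**Conclusion.** The concern holds for the pooled tests and mainly for two tables. For Days 29–91 against Day 91, and to a lesser degree Days 15–28 against Day 28, a nominal 5% test can reject far more often with no effect of the event. Once about 30% of deaths carry a listed fatal SAE, rejection is about 59% and 29% with onset at death, or 47% and 12% with a mean 7-day lag. These figures rest on Protocol hazards, an assumed 15% background risk and an assumed share; the direction depends on the share not being very low. The primary log-rank analysis of overall survival is not affected.

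**What to change.** Amend SAP 7.3.7 as follows.

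- For Randomization–Day 7, Days 8–14 and Days 15–28, group by events with onset in the window, include only subjects alive at Day 7, 14 or 28 respectively, and tabulate survival after that landmark.
- Drop Days 15–28 against Day 28 survival, which has no follow-up after the window. Days 15–28 against Day 91 remains, with a Day 28 landmark.
- Replace Days 29–91 against Day 91 with a Cox model in which event onset is a time-dependent covariate. At minimum, present these two tables descriptively without p-values.
- Describe all results as associations. An SAE that starts shortly before death will still be strongly related to death under either method. The sequence is then in the right order, but the event is not thereby shown to be the cause.

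No new data are needed. The cost is SAP wording and some reprogramming, and cells become smaller because deaths within a window leave that window's table.
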